Subjects will be screened for eligibility at the last scheduled treatment visit of the previous double-blind trial. Subjects will sign a separate informed consent form (ICF) at the last scheduled treatment visit of the previous double-blind trial for participation in Trial 331-201-00195 before any procedures specific to the open-label trial are performed. The assessments from the last scheduled treatment visit of the previous double-blind trial will serve as the baseline measures for Trial 331-201-00195 for any assessment that is not new (unique) to the open-label trial. Medical history will be updated, if necessary. Informed consent cannot be obtained after the last scheduled treatment visit of the previous double-blind trial without all screening/baseline assessments being repeated. If a subject is unable to rollover immediately, up to 3 days may be permitted between the end of the double-blind trial and the start of IMP in the open-label extension trial; however, this must be discussed with the medical monitor (Note: assessments from the last scheduled treatment visit in the previous double-blind trial that are going to be used as the baseline measures for Trial 331-201-00195 will not need to be repeated if the subject enters Trial 331-201-00195 within 3 days).

Eligible subjects will receive up to 12 weeks of daily treatment with open-label brexpiprazole. A safety follow-up telephone contact or clinic visit will occur 21 (\pm 3) days after the last dose of brexpiprazole.

Trial Population:

The trial population will consist of eligible male and female subjects diagnosed with BPD and who, in the investigator's judgment, could potentially benefit from treatment with brexpiprazole for BPD according to the following criteria:

- Subjects who participated in a double-blind brexpiprazole BPD trial will be eligible for Trial 331-201-00195 if they have completed the last scheduled treatment visit of the previous double-blind trial and did not terminate early.
- Subjects must qualify for Trial 331-201-00195 at the last scheduled treatment visit of the previous double-blind trial and must be able to continue treatment without interruption between the double-blind and open-label trials (if a subject is unable to rollover immediately, up to 3 days may be permitted between the end of the double-blind trial and the start of IMP in the open-label extension trial; however, this must be discussed with the medical monitor).

Key Inclusion/Exclusion Criteria:

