8.7.2 Physical Examination

Physical examinations will be performed at the time points described in the schedule of assessments (Table 1.3-1).

A complete physical examination will consist of measurement of height and waist circumference and a review of the following body systems: head, eyes, ears, nose, and throat; thorax; abdomen; urogenital; extremities; neurological; and skin and mucosa. At screening/baseline, height will be measured with a stadiometer, measuring stick or tape. Repeat measurement of height is not required at the physical examinations scheduled for the Week 12/early termination (ET) visit. Waist circumference will be measured at each physical examination (screening/baseline and Week 12/ET), using the provided measuring tape. The following procedures will aid in the standardization of these measurements:

- The subject should be minimally clothed (ie, lightweight clothing; no heavy overgarments).
- Waist circumference should be recorded before a subject's meal and at approximately the same time at each visit.
- Measurement will be accomplished by locating the upper hip bone and the top of the right iliac crest and placing a weighted measuring tape in a horizontal plane around the abdomen at the level of the crest. Before reading the tape measure, the assessor should assure that the tape is snug, but does not compress the skin, and is parallel to the floor. The measurement is to be made at the end of a normal exhalation.²⁴

The investigator (or designee) is responsible for performing the physical examination. If the appointed designee is to perform the physical examination, he or she must be permitted by local regulations and his or her name must be included on the delegation of authority log. Whenever possible, the same individual should perform all physical examinations. Any condition present at the post-treatment physical examination that was not present at the baseline examination should be documented as an AE and followed to a satisfactory conclusion.

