The sample size is not based on statistical power considerations but on the number of subjects rolling over from the lead-in trials. The trial population will be derived from eligible subjects

who completed the previous double-blind brexpiprazole BPD trials. The number of eligible subjects will be limited by the number of subjects enrolled into the double-blind trials.

5 Data Sets for Analysis and Missing Data

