9.2.2 Metabolic Change

In addition to mean change from baseline, incidence of treatment emergent significant changes in fasting lipids, fasting glucose, and metabolic syndrome will be summarized by parent study treatment group using the following criteria.

Criteria for Treatment-Emergent Significant Change in Lipids and Glucose		
LAB PARAMETER	BASELINE ¹	ANYTIME POST BASELINE
LDL Direct, Fasting (MG/DL)	Borderline 100-<160	High ≥ 160
	Normal/Borderline <160	High ≥ 160
	Normal <100	Borderline/High ≥ 100
	Any Value	Increased ≥ 30
HDL Cholesterol, Fasting (MG/DL)	Normal ≥ 40	Low <40
	Any Value	Decreased ≥ 20
Triglycerides, Fasting (MG/DL)	Normal <150	High 200-<500
	Borderline 150-<200	High 200-<500
	Normal/Borderline <200	High 200-<500
	Normal <150	Borderline/High/Very High ≥ 150
	Any Value	Increased ≥ 50
Glucose Fasting, Serum (MG/DL)	Normal <100	High ≥ 126
	Impaired 100-<126	High ≥ 126
	Normal/Impaired <126	High ≥ 126
	Any Value	Increased ≥ 10

¹ BASELINE IS DEFINED AS THE LAST AVAILABLE MEASUREMENT PRIOR TO THE FIRST DOSE OF OPEN-LABEL IMP IN THE OPEN-LABEL TREATMENT PHASE.

Criteria for Treatment-Emergent Metabolic Syndrome	
DESCRIPTION	ANYTIME POST BASELINE ¹
Central Obesity	Waist Circumference $\geq 102\text{cm}(\text{MALE}), \geq 88\text{cm}(\text{FEMALE})$
Dyslipidemia	Triglycerides $\geq 150\text{mg/dl}$
Dyslipidemia	HDL $< 40\text{mg/dl}(\text{MALE}), < 50\text{mg/dl}(\text{FEMALE})$
Supine Blood Pressure	Systolic $\geq 130\text{mmHg}$ and Diastolic $\geq 85\text{mmHg}$

Criteria for Treatment-Emergent Metabolic Syndrome	
DESCRIPTION	ANYTIME POST BASELINE¹
Glucose Fasting, Serum	$\geq 100\text{mg/dl}$
Metabolic Syndrome	Met 3 Or More of the Above Criteria at a Visit

¹ BASELINE IS DEFINED AS THE LAST AVAILABLE MEASUREMENT PRIOR TO THE FIRST DOSE OF OPEN-LABEL IMP IN THE OPEN-LABEL TREATMENT PHASE.

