9.3 Physical Examination and Vital Signs

Summary statistics for changes from baseline in vital signs will be provided for the Safety Sample. By-patient listings will be provided for physical examination.

Potentially clinically relevant vital signs measurements identified in the open-label treatment phase for the Safety Sample will be listed and summarized. Criteria for identifying vital signs of potential clinical relevance are provided in [Appendix 1](#).

In addition, the change from baseline in weight, BMI, and waist circumference, and potentially clinically relevant abnormalities in weight, will also be summarized.

9.4 12-Lead ECG

Summary statistics and incidence of potentially clinically relevant changes will be provided for ECG parameters.

For the analysis of QT and QTc, data from three consecutive complexes (representing three consecutive heart beats) will be measured to determine average values. The following QT corrections will be used for reporting purposes in the clinical study report:

- 1) QTcB is the length of the QT interval corrected for heart rate by the Bazett formula:

$$\text{QTcB} = \text{QT}/(\text{RR})^{0.5}$$
 and
- 2) QTcF is the length of the QT interval corrected for heart rate by the Fridericia formula:

$$\text{QTcF} = \text{QT}/(\text{RR})^{0.33}$$
- 3) QTcN is the length of the QT interval corrected for heart rate by the FDA Neuropharm Division formula:
$$\text{QTcN} = \text{QT}/(\text{RR})^{0.37}$$

Potentially clinically relevant changes in the 12-lead ECG identified in the open-label treatment phase for the Safety Sample will be listed and summarized by treatment group. Criteria for identifying ECG measurements of potential clinical relevance are provided in [Appendix 3](#).

Categorical changes in ECG parameters during the open-label treatment phase will be summarized based on the following criteria:

Categorical Change Criteria in QT/QTc Parameters		
Classification	Category	Criteria
QT	New Onset (> 450 Msec)	New onset (>450 msec) in QT means a subject who attains a value > 450 msec during treatment period but not at baseline.
QTc *	New Onset (\geq 450 Msec for men and \geq 470 Msec for women)	New onset (\geq 450 Msec for men and (\geq 470 Msec for women) in QTc means a subject who attains a value \geq 450 Msec for men or \geq 470 Msec for women during treatment period but not at baseline.

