9.6 Suicidality Data

Suicidality will also be monitored during the study using the C-SSRS [CC1] [REDACTED] and will be summarized as number and percentage of subjects reporting any suicidal behavior, ideation, behavior by type (4 types), ideation by type (5 types) and treatment emergent suicidal behavior and ideation. Summary will be provided for the open-label treatment phase.

Suicidality is defined as report of at least one occurrence of any type of suicidal ideation or at least one occurrence of any type of suicidal behavior during assessment period (count each person only once).

Treatment emergent suicidal behavior and ideation is summarized by four types: Emergence of suicidal ideation, Emergence of serious suicidal ideation, Worsening of suicidal ideation, Emergence of suicidal behavior.

Emergence of suicidal behavior/ideation is defined as report of any type of suicidal behavior/ideation during treatment when there was no baseline suicidal behavior/ideation.

Emergence of serious suicidal ideation is defined as observation of suicidal ideation severity rating of 4 or 5 during treatment when there was no baseline suicidal ideation.

Worsening of suicidal ideation is defined as a suicidal ideation severity rating that is more severe than it was at baseline.

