- CT-8.8.2 Listing of Serious TEAEs or Deaths that Are Related or Probably Related to COVID-19 (Safety Sample)
- CT-8.9 Incidence of Treatment-Emergent Adverse Events of Special Interests (AESIs) by System Organ Class and MedDRA Preferred Term (Safety Sample)
- CT-9.1 Listing of Deaths
- CT-9.2 Listing of Serious Adverse Events
- CT-9.3 Listing of Discontinuations Due to Adverse Events
- CT-10.1 Criteria for Laboratory Test Values with Potential Clinical Relevance
- CT-10.2.1 Listing of Laboratory Test Values with Potential Clinical Relevance by Subject (Safety Sample)
- CT-10.2.2 Listing of Laboratory Test Values with Potential Clinical Relevance by Test (Safety Sample)
- CT-10.2.3 Incidence of Laboratory Test Values with Potential Clinical Relevance (Safety Sample)
- CT-10.3.1 Mean Change from Baseline in Clinical Laboratory Test Results - Serum Chemistry (Safety Sample)
- CT-10.3.2 Mean Change from Baseline in Clinical Laboratory Test Results - Hematology (Safety Sample)
- CT-10.3.3 Mean Change from Baseline in Clinical Laboratory Test Results - Urinalysis (Safety Sample)
- CT-10.3.4 Mean Change from Baseline in Clinical Laboratory Test Results - Prolactin, by Sex (Safety Sample)
- CT-10.3.5 Mean Change from Baseline in Clinical Laboratory Test Results - Other Tests (Safety Sample)
- CT-10.4.1 Incidence of Laboratory Test Values with Potential Clinical Relevance - Prolactin (Safety Sample)
- CT-10.4.2 Listing of Laboratory Test Values with Potential Clinical Relevance - Prolactin (Safety Sample)
- CT-10.5.1.1 Incidence of Treatment-Emergent Significant Change in Lipids (Safety Sample)
- CT-10.5.1.2 Listing of Treatment-Emergent Significant Change in Lipids (Safety Sample)
- CT-10.5.2.1 Incidence of Treatment-Emergent Significant Change in Glucose (Safety Sample)
- CT-10.5.2.2 Listing of Treatment-Emergent Significant Change in Glucose (Safety Sample)
- CT-10.5.3.1 Incidence of Treatment-Emergent Metabolic Syndrome (Safety Sample)

- CT-10.5.3.2 Listing of Treatment-Emergent Metabolic Syndrome (Safety Sample)
- CT-10.6 Incidence of Potentially Liver Injury Related Laboratory Test Abnormalities (Safety Sample)
- CT-10.7 Listing of Potentially Liver Injury Related Laboratory Test Abnormalities (Safety Sample)
- CT-11.1 Criteria for Potentially Clinically Relevant Abnormalities in Vital Signs
 - CT-11.2.1 Listing of Potentially Clinically Relevant Abnormalities in Vital Signs (Safety Sample)

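### SAP 9.2.2 labels metabolic syndrome treatment-emergent but sets no baseline condition, so unchanged baseline cases count as new; the triglyceride High rows also miss values of 500 mg/dL and above

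*SAP*

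**What the plan says.** SAP Section 9.2.2 states that "incidence of treatment emergent significant changes in fasting lipids, fasting glucose, and metabolic syndrome will be summarized by parent study treatment group", using two tables of criteria.

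- **Lipids and glucose.** This table has a baseline column and a post-baseline column. Every row states a baseline category or says that any baseline value qualifies.
- **Metabolic syndrome.** This table has only a description column and a post-baseline column. It lists five absolute thresholds (waist, triglycerides, HDL, supine blood pressure, fasting glucose), and a case is a subject who "Met 3 Or More of the Above Criteria at a Visit". A footnote says which measurement is the baseline, but no row uses it.

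The output is CT-10.5.3.1, with listing CT-10.5.3.2. SAP Section 12 titles it as an incidence of treatment-emergent metabolic syndrome in the Safety Sample.

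Elsewhere the SAP writes its emergence rules out. New-onset QT and QTc (Section 9.4) must occur "during treatment period but not at baseline". Emergent suicidal behaviour or ideation (Section 9.6) is a report "during treatment when there was no baseline suicidal behavior/ideation".

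In the lipid table, three triglyceride rows (baseline below 150, 150 to below 200, and below 200 mg/dL) define the post-baseline High state as 200 to below 500 mg/dL. A fourth row counts any move from below 150 to 150 or more, and a fifth counts any increase of at least 50.

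**The concern.** A subject who meets the same three criteria at baseline and at Week 12 satisfies the syndrome rule and is counted as treatment-emergent. The denominator is not limited to subjects at risk either.

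The rollover design makes this matter more. For direct rollovers, the Protocol Synopsis says: "The assessments from the last scheduled treatment visit of the previous double-blind trial will serve as the baseline measures for Trial 331-201-00195". A syndrome already present at that visit, including one acquired during the parent trial, would therefore be attributed to the open-label phase. Results are shown by parent treatment group, so a difference in baseline prevalence between groups would appear as a difference in emergent syndrome even if new onset were equal. Such a difference is plausible: Protocol Section 2.3 gives increased weight as the most frequent event on brexpiprazole (12.1%), and more frequent than on placebo. The documents give no metabolic syndrome rates, however.

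The triglyceride cap has a separate effect. A worse post-baseline value can drop out of the rows meant to count shifts to High.

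**Working it through.** There is no figure in the plan to reproduce; SAP Section 4 says "The sample size is not based on statistical power considerations but on the number of subjects rolling over from the lead-in trials". The check applies the criteria as written and then illustrates the size.

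**1. One unchanged subject.** Take a woman with waist 95 cm, triglycerides 170 mg/dL, HDL 45 mg/dL, supine blood pressure 118/76 mmHg and fasting glucose 92 mg/dL, identical at baseline and Week 12. She meets the waist (at least 88), triglyceride (at least 150) and HDL (below 50) criteria, which makes three. She is counted as treatment-emergent although nothing changed.

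**2. When the rule can be met.** Protocol Table 1.3-1 and Section 8.7.2 schedule waist circumference and laboratory tests only at screening/baseline and Week 12/ET. At Weeks 2, 4 and 8 only blood pressure is scheduled. Apart from unscheduled tests, CT-10.5.3.1 is therefore in effect the Week 12/ET prevalence.

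**3. Size.** Let p be baseline prevalence, s the proportion of baseline cases still present at Week 12/ET, and o the onset among baseline-negative subjects. The documents give none of these; all three are assumptions.

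- Reported as written: p·s + (1 − p)·o
- With a baseline condition and a baseline-negative denominator: o
- Pre-existing share of counted cases: p·s / [p·s + (1 − p)·o]

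The grid is p = 10 to 30%, s = 70 to 90%, o = 5, 10 and 20%. Its extremes are:

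| o (after fix) | Reported, p = 10%, s = 70% | Pre-existing share | Reported, p = 30%, s = 90% | Pre-existing share |
|---|---|---|---|---|
| 5% | 7.0 + 4.5 = 11.5% | 60.9% | 27.0 + 3.5 = 30.5% | 88.5% |
| 10% | 7.0 + 9.0 = 16.0% | 43.8% | 27.0 + 7.0 = 34.0% | 79.4% |
| 20% | 7.0 + 18.0 = 25.0% | 28.0% | 27.0 + 14.0 = 41.0% | 65.9% |

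The ratio of reported to fixed figure runs from 25.0/20 = 1.25 to 30.5/5 = 6.1. With no new onset at all, the table would still show p·s, that is 7 to 27%.

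**4. Spurious group difference.** Hold o = 5% and s = 90% in two parent groups with baseline prevalence of 10% and 20%. The reported figures are 9.0 + 4.5 = 13.5% and 18.0 + 4.0 = 22.0%. That is a gap of 8.5 percentage points with identical onset.

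**5. Triglyceride rows, applied as written (mg/dL).**

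| Baseline to post-baseline | High rows met | Other rows met | Total |
|---|---|---|---|
| 180 to 499 | 2 | increase of at least 50 | 3 |
| 180 to 500 | 0 | increase of at least 50 | 1 |
| 140 to 499 | 2 | to 150 or more; increase of at least 50 | 4 |
| 140 to 500 | 0 | to 150 or more; increase of at least 50 | 2 |

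The LDL (160 and above) and glucose (126 and above) High rows have no upper limit.

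**The case against.** **The title implies the condition.** The sentence introducing the criteria, the table title and the output title all say treatment-emergent, and the footnote defines a baseline. A programmer could reasonably add the exclusion. It is true that the result depends on how the rule is coded. But the SAP says the incidence will use these criteria, and they contain no exclusion. The same footnote sits under the lipid table, where a separate baseline column does the work. At best the result rests on an unwritten choice.

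**The multiplier reflects the chosen grid.** This stands. The documents support no particular prevalence, persistence or onset, and a different grid gives different figures. The algebra establishes the direction; the figures only show that the effect need not be small.

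**The triglyceride band is a category label.** The fourth row names a Very High class, so the capped rows do count shifts into High as defined. Values of 500 and above are not lost: from any baseline below 200 the rise exceeds 300, so the row for an increase of at least 50 always catches it. A baseline below 150 is also caught by the row for 150 or more, and Appendix 2 flags the value. What remains is narrower. The High rows understate shifts to High or worse, and no row isolates 500 and above.

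**It is one descriptive table.** This is also true. Mean changes and baseline-conditioned lipid and glucose shifts are reported separately, and the primary analysis does not use this table.

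**Conclusion.** The concern holds. As written, the criteria for treatment-emergent metabolic syndrome produce post-baseline prevalence, and CT-10.5.3.1 would present persistent baseline cases as new ones. The direction is certain whenever any baseline case persists and the persistence proportion exceeds the onset rate. The amount is unknown; over the assumed grid the reported figure is 1.25 to 6.1 times the onset among baseline-negative subjects. This assumes the table is programmed as specified.

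The triglyceride point also holds but is secondary: a shift from below 200 to 500 mg/dL or more is missed by all three High rows, though other outputs still capture it.

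Both faults should be fixed because the tables would not mean what their labels say. They affect secondary descriptive safety outputs only; the primary analysis of adverse event frequency and severity is untouched.

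**What to change.** **Metabolic syndrome.** Add a baseline condition to the table: fewer than three criteria met at baseline. Use as denominator the baseline-negative subjects with post-baseline data, and show baseline prevalence beside the result for each parent group and overall. Alternatively, retitle CT-10.5.3.1 and CT-10.5.3.2 as post-baseline prevalence and show baseline prevalence alongside.

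**Incomplete baselines.** State how a subject with a missing or nonfasting baseline component is classified. One workable rule is positive if at least three evaluable criteria are met, negative if the criteria met plus those not evaluable total fewer than three, and otherwise unclassifiable and reported separately.

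**Triglycerides.** Change the post-baseline state in the three High rows to 200 mg/dL and above, or keep the band and add matching rows for 500 and above.

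**Cost.** SAP wording and table logic only; waist, laboratory tests and vital signs are already scheduled at screening/baseline and Week 12/ET. The syndrome denominator becomes smaller. The rule for incomplete baselines is needed because Protocol Table 1.3-1 and Section 8.7.1 allow nonfasting baseline blood with a discretionary repeat at the next visit, which falls after dosing has started and so cannot serve as baseline under SAP Section 7.1. Retitling avoids the need to classify subjects as baseline-negative, but then the table no longer reports new onset.

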9.3 Physical Examination and Vital Signs

Summary statistics for changes from baseline in vital signs will be provided for the Safety Sample. By-patient listings will be provided for physical examination.

Potentially clinically relevant vital signs measurements identified in the open-label treatment phase for the Safety Sample will be listed and summarized. Criteria for identifying vital signs of potential clinical relevance are provided in [Appendix 1](#).

In addition, the change from baseline in weight, BMI, and waist circumference, and potentially clinically relevant abnormalities in weight, will also be summarized.

9.4 12-Lead ECG

Summary statistics and incidence of potentially clinically relevant changes will be provided for ECG parameters.

For the analysis of QT and QTc, data from three consecutive complexes (representing three consecutive heart beats) will be measured to determine average values. The following QT corrections will be used for reporting purposes in the clinical study report:

- 1) QTcB is the length of the QT interval corrected for heart rate by the Bazett formula:

$$\text{QTcB} = \text{QT}/(\text{RR})^{0.5}$$
 and
- 2) QTcF is the length of the QT interval corrected for heart rate by the Fridericia formula:

$$\text{QTcF} = \text{QT}/(\text{RR})^{0.33}$$
- 3) QTcN is the length of the QT interval corrected for heart rate by the FDA Neuropharm Division formula:
$$\text{QTcN} = \text{QT}/(\text{RR})^{0.37}$$

Potentially clinically relevant changes in the 12-lead ECG identified in the open-label treatment phase for the Safety Sample will be listed and summarized by treatment group. Criteria for identifying ECG measurements of potential clinical relevance are provided in [Appendix 3](#).

Categorical changes in ECG parameters during the open-label treatment phase will be summarized based on the following criteria:

Categorical Change Criteria in QT/QTc Parameters		
Classification	Category	Criteria
QT	New Onset (> 450 Msec)	New onset (>450 msec) in QT means a subject who attains a value > 450 msec during treatment period but not at baseline.
QTc *	New Onset (\geq 450 Msec for men and \geq 470 Msec for women)	New onset (\geq 450 Msec for men and (\geq 470 Msec for women) in QTc means a subject who attains a value \geq 450 Msec for men or \geq 470 Msec for women during treatment period but not at baseline.
	New Onset (\geq 450 Msec for men and \geq 470 Msec for women) And > 10% Increase	New onset (\geq 450 Msec for men and \geq 470 Msec for women) and > 10% increase in QTc means a subject who attains a value \geq 450 Msec for men or \geq 470 Msec for women, and > 10% increase during treatment period but not at baseline
	New Onset (> 500 Msec)	New onset (> 500 msec) in QTc means a subject who attains a value > 500 msec during treatment period but not at baseline.
	Increase 30 - 60 Msec	Increase from baseline value > 30 and \leq 60 msec in QTc
	Increase > 60 Msec	Increase from baseline value > 60 msec in QTc

* QTc categorical change criteria apply to QTcB, QTcF and QTcN.

